Negative Syndrome Scale																
(PANSS) ^k																
Clinical Site Admission ^a		X											X			

Table 2: Schedule of Assessments (Continued)

Study Period	Screen	Wash	nout/Taper ^a				Treatm	ent/C	bservat	tion ^a			Re	stabilizati	on ^a	Follow-up
Study Day	-35 to -13	-12	-11 to -9	-8	-7	-6	-5 to -1	1	2-8	9-14	15	22	29	30-32	33	61 ± 2
Procedures/Assessments																
Awaken Subject			X	X	X	X	X	X	X	X	X	X	X	X	X	
Provide Meals ¹		X	X	X	X	X	X	X	X	X	X	X	X	X	X	
Randomize Subject								X								
Dispense Oral Lurasidone					X	X										
Oral Lurasidone Administration ^m					X	X										
Dispense Lurasidone or Placebo Injection								X								
Lurasidone or Placebo Injection Administration								X								
Investigator Injection Site Safety Assessment ⁿ								X	X	X	X	X	X			
Subject Injection Site Pain Assessment ^o								X	X		X	X	X			
Schedule Next Visit	X										X	X			X	
Clinical Site Discharge ^p											X	X			X	
Concomitant Medications ^q	X	X	X	X	X	X	X	X	X	X	X	X	X	X	X	X
Pretreatment Events	X	X	X	X												
Adverse Events ^r					X	X	X	X	X	X	X	X	X	X	X	X

Note: Subjects who discontinue the study prior to Day 29 will undergo assessments scheduled for Day 29 at the time of discontinuation. Subjects who discontinue the study after Day 29 but prior to Day 61 will undergo assessments scheduled for Day 61 at the time of discontinuation.

- Day -12 and Day -8: once daily
- Days -7 and -6: predose and 2 hours postdose
- Day -1
- Day 1 pre-injection dose and 6 and 12 hours post-injection dose
- Days 3, 5, 7, 9, 11, 13, and 15 (time-matched to the predose timepoint on Day 1), and Days 22, 29, and 33 (approximately time-matched to the predose timepoint on Day 1), and Follow-up.

^a Eligible subjects must be washed out/tapered off of their current antipsychotic medications within 5 to 6 half-lives prior to Day -8 (may begin Day -19). Mandatory inpatient periods are Day -12 to Day 15 (for treatment and observation) and Day 29 to Day 33 (for restabilization to previous medications; restabilization begins Day 29). Subjects may remain inpatient until Day 33 at the Investigator's discretion.

b Vital signs = Blood pressure (supine and standing), pulse rate (supine and standing), respiration rate, and body temperature will each be collected at the following times

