- Note: Supine blood pressure and pulse rate should be collected at the same time as 12-lead ECG (when 12-lead ECG is collected for the same timepoint). A window of \pm 10 minutes of scheduled time is allowed. After Cohort 1, timepoints for vital signs may be changed based on observed t_{max} of Lurasidone injectable suspension and its metabolites.
- ^c Standard 12-lead ECGs will be collected at Screening and during the washout/taper period on Days -12 and -8. On Days -7 and -6, standard 12-lead ECGs will be collected predose and 2 hours postdose. Standard 12-lead ECGs will be collected predose and 6, and 12 hours post injection dose on Day 1 and on Days 3, 5, 7, 9, 11, 13, and 15 (time-matched to the predose timepoint on Day 1), and Days 22, 29, and 33 (approximately time-matched to the predose timepoint on Day 1), and Follow-up. A window of ± 15 minutes of scheduled time is allowed for ECGs performed up to and including Day 15. After Cohort 1, these timepoints may be changed based on observed t_{max} of Lurasidone injectable suspension and its metabolites.

^d Hematology, Serum Chemistry, Urinalysis, Lipid Panel, Coagulation Panel, and Thyroid Panel.

- Subjects are to fast ≥ 8 hours prior to blood sample collection for clinical laboratory tests.
- Blood samples will be collected for Hematology and Serum Chemistry at screening, Day -8, Day 1 injection predose, Days 8 and 15 (time-matched to the predose timepoint on Day 1), and Days 22, 29, and 33 (approximately time-matched to the injection predose sample on Day 1), and follow-up. A window of ± 10 minutes is allowed for clinical laboratory test sample collection. Samples will be obtained at the same time that other blood and urine samples are taken whenever possible.
- Blood samples for thyroid panel, coagulation panel, and lipid panel will be collected at Screening, Day -8, Day 1 injection predose, Day 15 (time-matched to the predose timepoint on Day 1), and Day 29 (approximately time-matched to the injection predose sample on Day 1).
- Urinalysis will be collected at screening, Day -8, Day 1 injection predose (time-matched to the predose timepoint on Day 1), Days 8 and 15 (time-matched to the predose timepoint on Day 1), and Days 22, 29, and 33 (approximately time-matched to the injection predose sample on Day 1), and follow-up.

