- Serum Prolactin levels will be blinded, except at screening and Day 1. Designated unblinded medical site staff will be notified if prolactin concentrations are > 200 ng/mL. Blood samples will be collected on Day -8, Day 1 injection predose, Days 8 and 15 (time-matched to the predose timepoint on Day 1), and Days 22, 29, and 33 (approximately time-matched to the injection predose timepoint on Day 1), and follow-up.
- f Blood samples for serum PK assessment will be collected at predose and 2 hours postdose on Days -7 and -6, and then at 0 hour (predose), 2, 4, 6, 12, 24, 48, 72, 96, 120, 144, 336, 504, 672, and 1440 (± 48) hours after the injection dose given on Day 1. A window of ± 5 minutes of scheduled time (up to 8 hours postdose), and ± 10 minutes of scheduled time (from 12 hours postdose onward) is allowed. Blood sampling timepoints for PK assessment for subsequent cohorts may be modified based on serum concentration data from initial cohort(s). Evaluation of the relationship between the timing of below limit of quantification (BLQ) and the elimination half-life will be used to justify the revised blood sampling for PK and safety assessment schedule.
- Urine samples for PK assessment will be collected at the following intervals: -0.5 to 0 hour (predose); 0 to 24, 24 to 48, 48 to 72, 72 to 96, 96 to 120, and 120 to 144 hours after the injection dose given on Day 1, and recording of the volume of urine sample at each time interval. Urine samples collected for PK analysis may also be used for the additional characterization and/or bioanalytical method development of putative metabolites of DSP-1349M and for biomarker measurement, if needed.
- h Tapering of patient's psychotropic medications prior to entry to the study has been done routinely in previously conducted studies with lurasidone. The exact timing and method of taper will depend on the subject's medication regimen, but the tapering process will typically start approximately one week prior to Day -12 admission. However, for some subjects, the tapering process will begin sooner than one week and some may begin later than one week from Day -12 admission based on PI's evaluation.

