6.3.2. Rationale for the Dosages

Dosing for the lurasidone injectable suspension formulation is based on the amount in mg of lurasidone present at the injection site following IM administration, which was $\sim\!60$ mg at the lowest dose of 7.5 mg/kg in the dog. There was no no-observed-adverse effect level determined in the dog; therefore a 2-fold reduction in the amount of lurasidone at the injection site was recommended, which is equal to 30 mg. At the clinical formulation's fixed concentration of 150 mg/mL, this dose will be an injection volume of 0.2 mL.

A 2-fold reduction is considered appropriate because the primary finding of granuloma is common following IM administration of an irritating substance. Clinicians are familiar with appropriate monitoring. This finding is reversible and non-lethal. The pharmacology of lurasidone is well known, and systemic findings in humans have been characterized over a range of serum concentrations.

After the lurasidone injectable suspension starting dose of 30 mg, dose escalation will be as follows: 75, 150, 300, 450 mg for a single IM injection. A 6 week monitoring period for adverse events will be employed in this study. In animals, the injection site findings were apparent within 1 week and findings persisted for an additional week before beginning to resolve. Therefore, if no injection site findings are seen within 2 weeks and no other stopping criteria are met, dose escalation may proceed.

Projection of PK following each cohort indicates that C_{max} will not exceed 348 ng/mL. This value is the C_{max} at 400 mg orally, which is the MTD (Study D1050217, Day 6). It is unlikely that IM administration will exceed this concentration as the depot will absorb more slowly than following oral administration. Therefore, routine safety monitoring will be utilized to determine stopping criteria.

In order to ensure subjects who are unable to tolerate lurasidone do not receive the lurasidone injectable suspension formulation, subjects will be evaluated for tolerability after administration of oral lurasidone 80 mg for 2 days (ie, two doses) prior to lurasidone injectable suspension administration.

The oral lurasidone 80 mg dose was previously established as the maximum tolerated dose (MTD) in healthy subjects. In subjects with schizophrenia, an oral lurasidone dose of 400 mg/day was previously established as the MTD.

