10.5.3.5. Days 2 to 8 (Safety and Tolerability Observation)

The following study related procedures will be performed:

- Awaken Subject (daily).
- Provide Meals (daily).
- Subject Injection Site Pain Assessment on Days 2 and 8.
- Investigator Injection Site Safety Assessment (daily).
- Obtain Vital Signs on Days 3, 5, and 7(time-matched to the injection predose timepoint on Day 1).
- Perform 12-Lead ECG on Days 3, 5, and 7 (time-matched to the injection predose timepoint on Day 1).
- Collect Blood and Urine Samples for Clinical Laboratory Tests on Day 8 (time-matched to the injection predose timepoint on Day 1):
 - Hematology
 - Serum Chemistry
 - Urinalysis
- Obtain Blood Sample for Serum Prolactin (Day 8).
- Collect Blood Sample for PK at 24, 48, 72, 96, 120 and 144 hours post-injection dose.
- Collect Urine Sample for PK at 24 to 48, 48 to 72, 72 to 96, 96 to 120, and 120 to 144 hours post-injection dose.
- Administer C-SSRS on Day 7.

- Administer PANSS on Day 8.
- Record Concomitant Medications (daily).
- Record Adverse Events (daily).

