5	96 hours post-injection dose						
6	120 hours post-injection dose						
7	144 hours post-injection dose						
15	336 hours post-injection dose						
22	504 hours post-injection dose						
29	672 hours post-injection dose						
61	1440 hours post-injection dose						

COLLECTION REQUIREMENTS

Collect 4 mL blood sample into a serum separator tube and allow to clot for 30 to 60 minutes at room temperature before centrifugation. The samples will be centrifuged within 1 hour of collection at approximately 2000 g for 10 minutes at approximately 4°C, preferably. To ensure a more homogenous sample, serum sample should first be transferred to 1 tube and mixed well, then split the sample with approximately equal volume into 2 appropriate cryovials/tubes, and label as PKS-Set 1 and PKS-Set 2. Store serum vials at approximately -20°C freezer within 1 hour until shipping to the bioanalytical lab. The date and time of blood collection must be recorded.

URINE SAMPLES

Urine samples must be collected from all subjects at the time points indicated below.

To prevent lurasidone nonspecific binding to collection devices, urine samples may be treated with an additive after each void.

Detailed instructions on urine sample collection and treatment after each void will be provided in a Laboratory Manual.

Day No.	Time Interval Relative to Lurasidone or Placebo Injection Dosing
1	Predose -0.5 to 0 hour
1/2	0 to 24 hours post-injection dose
2/3	24 to 48 hours post-injection dose
3/4	48 to 72 hours post-injection dose
4/5	72 to 96 hours post-injection dose
5/6	96 to 120 hours post-injection dose
6/7	120 to 144 hours post-injection dose

The date and time of sample collection must be recorded.

Transfer each individual void/collection in the labeled timepoint storage collector.

Store samples in a freezer at approximately -20°C until shipping to the bioanalytical lab.

Very important: Do not fill containers/tubes more than 75% of total volume to allow for volume expansion during freezing. Overfilled containers will burst!

SHIPPING:

- Set 1 and Set 2 samples will be shipped in 2 separate shipments to the appropriate laboratory.
- Freeze samples for at least several hours before shipping to the appropriate laboratory.
- All samples will be shipped with dry ice protection.

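### No serum PK sample is scheduled between 144 h and 336 h after injection; if the depot peaks in that gap, tmax cannot be located and Cmax and AUC are understated

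*Protocol*

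**What the plan says.** Protocol Table 2, footnote f sets the post-injection serum PK times at "0 hour (predose), 2, 4, 6, 12, 24, 48, 72, 96, 120, 144, 336, 504, 672, and 1440" hours. The gap lies in the last part of that list, "96, 120, 144, 336, 504, 672, and 1440". Section 10.5.3.5 (Days 2 to 8) agrees: "Collect Blood Sample for PK at 24, 48, 72, 96, 120 and 144 hours post-injection dose". Section 10.5.3.6 (Days 9 to 14) lists no PK draw. Appendix III and SAP 17.1.1 go from "144 hours post-injection dose" on Day 7 straight to "336 hours post-injection dose" on Day 15.

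Subjects are in the clinic over this interval: "Mandatory inpatient periods are Day -12 to Day 15 (for treatment and observation". Section 10.5.3.5 schedules laboratory and prolactin blood on Day 8, time-matched to the Day 1 predose time. Table 2, footnote c puts ECGs on "Days 3, 5, 7, 9, 11, 13, and 15 (time-matched to the predose timepoint on Day 1".

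Cmax, tmax, AUC0-last and AUC0-inf are the primary PK parameters (Protocol 14.3.6, SAP 17.2). Cmax and tmax are read directly from the observed concentrations (Protocol 10.3, SAP 17.2.1). The Safety Review Team (SRT) must review at least 14 days of exposure data before the next dose level (Protocol 9.2), and SAP 5.1 includes PK parameters in that review.

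Footnote f and Section 10.3 allow PK times to change for later cohorts. Footnotes b and c allow vital-sign and ECG times to be reset to the observed tmax.

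**The concern.** Section 3.1 describes release from muscle as governed by dissolution. Section 6.3.2 expects slower uptake than from the tablet: "It is unlikely that IM administration will exceed this concentration as the depot will absorb more slowly than following oral administration". Section 14.1 says there are no earlier human PK data for the formulation, and neither document gives an expected tmax or half-life after injection. The plan therefore gives no basis for ruling out a peak on Days 8 to 14, the stretch with no PK sample.

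Cmax and tmax are primary parameters with no interpolation, and the AUCs must bridge the gap with one trapezoid. An in-gap peak would distort these summaries, the exposure information given to the SRT, and any ECG times later reset to the observed tmax. The ECGs on Days 9, 11 and 13 have no paired concentration.

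**Working it through.** **Schedule.** Day = 1 + h/24 reproduces the plan's own mapping: 144/24 + 1 = 7, 336/24 + 1 = 15, 1440/24 + 1 = 61. The gap is 336 − 144 = 192 h. Intervals are 24 h just before it and 168 h just after it (504 − 336).

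**Assumptions.** The documents give no tmax or peak shape, so both are assumed. True tmax is placed anywhere from 145 to 335 h. The noise-free curve is C/Cmax = [(t/tmax)·exp(1 − t/tmax)]^n. n = 1 is first-order release with equal absorption and elimination rates, a broad peak. Larger n gives a sharper, delayed peak.

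**Worst position.** The two flanking samples are equally high when tmax = 192 / ln(336/144) = 226.6 h. With a true tmax of about 227 h, the observed value is 144 h (227 − 144 = 83 h early) or 336 h (336 − 227 = 109 h late). This holds for every n.

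**Cmax at that position.** For n = 1, (336/227)·exp(1 − 336/227) = 0.916, so Cmax is 8.4% low. For other n, raise 0.916 to the power n. The last column repeats the search for the worst position with 168 h and 240 h added.

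| n | Cmax low by, current times | Cmax low by, with 168 h and 240 h |
|---|---|---|
| 1 | 8.4% | 1.6% |
| 2 | 16.1% | 3.1% |
| 3 | 23.2% | 4.6% |
| 5 | 35.6% | 7.6% |
| 10 | 58.5% | 14.6% |

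These are worst cases. For n = 1 the error is about 1% at a true tmax of 168 h and 0.3% at 312 h. First-order curves with unequal rates lose less: at a true tmax of 216 h, 7.0% at a rate ratio of 1 and 5.1% at a ratio of 10.

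**Second model, also assumed.** One compartment, elimination half-life 20 or 40 h, Weibull release with shape 1 to 4 and scale 200 to 480 h.
- Shape 1 (first order): tmax is 65 to 139 h, always before the gap. Cmax error is at most about 0.5% and AUC0-672 error is under 2%.
- Profiles with true tmax of 170 to 285 h: Cmax is low by 2–3% up to 59%, and AUC0-672 by about 3% to 51%. With 168 h and 240 h added, the Cmax error is at most about 13% and the AUC0-672 error at most about 11%.
- Example (half-life 20 h, scale 240 h, shape 3, true tmax about 236 h): Cmax is 44% low and AUC0-672 28% low on the current times, and 0.1% and 7.6% low with the two samples added.

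**Dose proportionality.** An equal proportional error at every dose leaves the power-model slope unchanged. If only 300 and 450 mg were affected, the slope over the five planned doses would read 1 + 0.424·ln(1 − e), where 0.424 is the sum of the centred log doses for those two levels (1.996) divided by the sum of squares (4.706). A true slope of 1.00 then reads 0.96, 0.91 or 0.85 for e = 8%, 20% or 30%.

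**The case against.** **The peak may not be in the gap.** Slow release is not the same as delayed release. With first-order release and the half-lives assumed above, a peak after 144 h needs a release half-life above about 370 h (elimination 40 h) or 2,800 h (elimination 20 h). The large errors come from delayed-release shapes that nothing in the documents establishes. This stands. A reader might infer that the plan misses the peak; the documents support only that it would if the peak falls there.

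**The times can be adapted.** A reader might also infer that Cohort 1 data could never reveal an in-gap peak. That goes too far. In the worked example, concentrations at 96, 120, 144 and 336 h are 24%, 39%, 56% and 53% of the true Cmax. A curve still climbing at 144 h with a similar level at 336 h signals a peak between them. The signal arrives at the lowest planned dose, before escalation, and the SRT also reviews exposure at 28 days. But it flags the peak without measuring it, and Cohort 1's Cmax and tmax stay unrecoverable. The change is optional, and its stated justification is the timing of values below quantification against half-life, not tmax. The SAP of 11APR2019 keeps the times and reports no change in conduct (4.5); that fits equally well with data that gave no reason to change.

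**Escalation.** It is tempting to conclude that a safety limit could be passed unseen, because Section 6.3.2 projects Cmax to stay within 348 ng/mL. Section 9.3 sets no numeric exposure limit, and Section 6.3.2 leaves stopping to routine safety monitoring. Even with a 44% error, concealing a true value above 348 ng/mL would need an observed value above about 348 × 0.56 = 195 ng/mL. ECGs and daily injection-site checks continue through the gap.

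**Conclusion.** The concern holds conditionally. The 192 h gap is certain and consistent across both documents. Whether the peak falls in it is unknown.

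If it does, the tmax error does not need a sharp peak: up to about 83 to 109 h for a mid-gap peak. The Cmax error does depend on shape: under about 10% for a broad first-order peak, and roughly 15% to over 50% near the worst position for the assumed sharper shapes. AUC across the gap is understated too. If the peak falls before 144 h, little is lost. All percentages rest on assumed curves, because the documents supply none.

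For escalation, the consequence is less reliable exposure information for the SRT, not a missed stopping rule. The change is worth making because it is cheap, it sharply reduces the mid-gap error, and the adaptation clause is only a partial safeguard.

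**What to change.** From Cohort 1, add a PK tube at 168 h (Day 8, with the existing laboratory draw) and a PK sample at 240 h (Day 11, at the existing ECG and vital-sign time). Amend the Table 2 PK row and footnote f, Protocol 10.5.3.5, 10.5.3.6 and Appendix III, SAP 17.1.1, and the visit list in SAP Appendix 2, which also goes from Day 7 to Day 15.

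The longest interval between 144 h and 336 h falls from 192 h to 96 h (240 to 336 h).

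Cost: one extra 4 mL tube, at most one inpatient venepuncture per subject, and the assays. No visit is added. To avoid the extra venepuncture, the 120 h sample can be moved to 240 h. No ECG is paired with 120 h (Day 6), and AUC0-144 remains derivable. The trade-off is small: for a true peak at 120 h, the 144 h sample reads 1.2·exp(−0.2) = 0.982 of Cmax when n = 1 (1.8% low), and 0.982^5 = 0.915 when n = 5 (8.5% low).

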2. LIST OF ABBREVIATIONS AND DEFINITIONS OF TERMS

The abbreviations and the definition of key study terms used in the clinical study protocol are shown in Table 3 and Table 4.

Table 3: List of Abbreviations

Abbreviation	Full Form
AE	Adverse event
ALT	Alanine aminotransferase
AST	Aspartate aminotransferase
ATC	Anatomical Therapeutic Chemical
BMI	Body mass index
CFR	Code of Federal Regulations
CI	Confidence Interval
CLIA	Clinical Laboratory Improvement Amendments
CRF	Case report form (or electronic case report form)
CRO	Contract research organization
C-SSRS	Columbia-Suicide Severity Rating Scale
CV	Coefficient of variation
ECG	Electrocardiogram
EDC	Electronic data capture
EPS	Extrapyramidal symptoms
FDA	U.S. Food and Drug Administration
GCP	Good Clinical Practice
hCG	Human chorionic gonadotropin
ICF	Informed consent form
ICH	International Council on Harmonisation
IEC	Independent Ethics Committee
IND	Investigational New Drug
IPD	Important protocol deviation
IRB	Institutional Review Board
IUD	Intrauterine device
IXRS	Interactive Voice/Web-based Response System
MedDRA	Medical Dictionary for Regulatory Activities

Table 3: List of Abbreviations (continued)

Abbreviation	Full Form
MMRM	Mixed model for repeated measures
PANSS	Positive and Negative Syndrome Scale
PK	Pharmacokinetic(s)
PR	Time between P wave and QRS in electrocardiography
PT	Preferred term
PVG	Pharmacovigilance
QRS	Electrocardiographic wave (complex or interval)
QT	Electrocardiographic interval from the beginning of the QRS complex to the end of the T wave
QTc	QT interval corrected for heart rate
SAE	Serious adverse event
SAP	Statistical analysis plan
SOC	System organ class
SOP	Standard Operating Procedure
SRT	Safety review team
US	United States

Table 4: Definition of Key Study Terms

Terms	Definition of terms
CRF	A printed, optical, or electronic document designed to record all of the protocol required information to report to the Sponsor for each study subject.
Screened Subject	Any subject who signed the study specific informed consent and completed at least one study related procedure.
Screen Failures	Any subject who signed the study specific informed consent but either failed to meet study requirements during screening or met study requirements at screening but was not enrolled/randomized.
Study Drug (or Study medication)	Term to cover investigational drug, placebo, and/or active control.
Treatment Period	The period of the study in which the study drug is administered.
Randomized Subject	Any subject who was randomized into the treatment period of the study and was assigned a randomization number.
Enrolled Subject	Any subject who was successfully screened and enrolled into the pre-randomization period of the study.
Randomization Failures	Any subject who was enrolled but not randomized.
Completed Subject	Any subject who participated throughout the duration of the study, up to and including Day 29.
Early Termination Subject	Any subject who was successfully screened and randomized into the treatment period of the study, but did not complete the study.
End of Treatment	The day that the subject receives the protocol-defined last dose of the study drug.
End of Study	The day of the last visit by the last subject in the study.

